3.0 Protocol Objectives

The main objective of this study is to collect safety data to examine whether MDMA-assisted therapy will be tolerated and to estimate effect size of symptom reduction in social anxiety that is common in the adult autistic population as evaluated by standard clinical measures.

3.1 Primary Objective:

To estimate effect sizes of social anxiety symptom reduction between MDMA and placebo, as measured by the clinician-administered LSAS administered by a blinded IR, at baseline, one day, two weeks, and one month after each experimental session, and at 6-month follow-up.

3.2 Secondary Objectives:

The following objectives will compare MDMA subjects to placebo subjects in Stage 1:

- To assess effects on levels of OT, AVP, and CORT in peripheral blood at baseline, once during each experimental session between hours 2 – 3, one month after the second experimental session, and at 6-month follow-up.
- To assess effects on social perception using The Awareness of Social Inference Test (TASIT) at baseline, once during each experimental session between hours 2 – 3, one month after the second experimental session, and at 6-month follow-up.
- To assess effects on emotion labeling using the Toronto Alexithymia Scale-20 (TAS-20) at baseline, one month after each experimental session, and 6-month follow-up.
- To assess effects on emotion regulation using the Emotion Regulation Questionnaire (ERQ) at baseline, one month after each experimental session, and 6-month follow-up.
- To assess effects on depression symptoms as measured by the Beck Depression Inventory-II (BDI-II) at baseline, one day, two weeks, one month after each

- experimental session, monthly by mail during the 5 months leading up to the 6-month follow-up assessment.
- To assess effects on perceptions of stress as measured by the Perceived Stress Scale (PSS) at baseline, within 24 hours after each experimental session, one month after each experimental session and monthly by mail leading up to the 6-month follow-up assessment.
 - To assess effects on four aspects of empathy, as measured by the Interpersonal Reactivity Index (IRI) at baseline, within 24 hours after each experimental session, one month after each experimental session, and at the 6-month follow-up assessment.

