5.2 Study Procedures and Visit Descriptions

5.2.1 Prescreening and Screening

The therapist team for this study will consist of the PI, [name]., and co-investigator [name]. Candidate, and all study visits will be completed at Harbor-UCLA Medical Center. Prospective subjects will be prescreened by telephone or email according to an IRB-approved script to learn if they meet basic eligibility criteria. All individuals who are prescreened should be assigned a screening number and recorded on the Subject Screening Log where information on the selection of potential subjects in the trial should be collected.

Upon signing the IRB-approved informed consent form (ICF), the potential subject may commence study-related screening activities. The screening number should also be recorded on the signed ICF. If a subject is enrolled, the study staff should record the enrollment date and assign a subject number. If a subject is not enrolled, an explanation should be recorded on the Screening Log. A CRF will not be completed for subjects who are not enrolled. These subjects will only be documented on the Screening Log and Source Records. It is the responsibility of the PI to file the Screening Log in the investigator site file (ISF) to be readily available for on-site monitoring and/or inspection by relevant authorities. Screening may take place over more than one day and should be complete by up to two months prior to enrollment. If, after reviewing all information, the PI concludes that a subject is eligible, they will enroll the subject in the study. Visits will be scheduled consecutively, as described in the Time and Events Table.

- a. Explain and obtain written informed consent from the subject and Support Partner. Written informed consent must be obtained from the subject prior to performing any tests or evaluations for the study.
- b. Assign the subject a screening number. Complete the Screening Log.
- c. Review the ability of females of childbearing potential to become pregnant and their commitment to practice appropriate birth control, as determined by the PI for the treatment period of the study.
- d. Collect perceptions about the study using the Feedback Questionnaire.
- e. Administer C-SSRS to assess suicide risk.
- f. Administer the SCID-I-RV to assess co-morbid psychological disorders.
- g. Administer ADOS-2, Module 4 to confirm autistic status.
- h. A blinded IR will administer the LSAS.
- i. Obtain medical and psychological history by interview.

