- d. The therapists will inquire about any possible changes in the subject's health to ensure that subject continues to meet eligibility criteria and, if applicable, will confirm that the subject has appropriately tapered off of medications.
- e. The subject and therapists will discuss goals for the experimental session and will review what will happen during the experimental session.
- f. During one of the preparatory sessions, the therapists will introduce the subject to the staff at the outpatient research center who they will be most likely to encounter before, during, or after treatment sessions.
- g. The Support Partner will meet with the therapists prior to the first experimental session to review and confirm their role and responsibilities and sign an ICF addendum. There must be mutual agreement between the subject and therapists concerning the presence of the Support Partner.
- h. The therapists will administer the C-SSRS just prior to beginning the second preparatory session, unless a subject is still undergoing medication washout. Subjects still undergoing medication washout will complete the C-SSRS during the second preparatory session or at a point after washout is complete prior to the first experimental session.
- i. Assess general wellbeing at each preparatory session.
- j. At the end of the first preparatory session, subjects will complete:
 - a. BDI-II
 - b. STAI
 - c. PSS
 - d. IRI

- e. RSES
- k. At the end of the second preparatory session, subjects will complete the TASIT.
- l. The second preparatory session will include a comprehensive tour of the treatment location and introductions to all available research and support personnel who subjects are likely to see during experimental sessions.
- m. At the end of the third preparatory session, subjects will complete:
 - a. ERQ
 - b. TAS-20
 - c. QoL-Q
- n. During the third and last preparatory session, give the Reminder of Study Rules to the subject, which includes instructions and restrictions for conduct prior to receiving the drug. Subjects must agree to:
 - Refrain from eating after 24:00 (midnight) the evening before the experimental session.
 - Ingest only alcohol-free liquids after 24:00 (midnight) the evening before the experimental session.
 - Refrain from the use of any psychoactive drug, with the exception of caffeine or nicotine, within 24 hours of each experimental session.

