- r. The subject will sit or recline on comfortable furnishings. Eyeshades and a program of music will be provided if the subject wishes to use them. Subjects may speak to the therapists whenever they wish, who will provide guidance and support, as needed.
- s. Measure BP, pulse, and BT once every hour throughout the experimental session. More frequent measures will be taken if clinical signs and symptoms of hypertension are observed. If BP values are sustained at 180 systolic and/or 110 diastolic, the PI will make a decision about whether to conduct additional measurements or to provide treatment. Measurements may be repeated until they have been decreasing for 15 minutes or have stabilized at a level judged by the PI to be safe.
- t. After the first hour, if the subject has not spoken spontaneously, check in with him/her about the nature of the experience. For the rest of the experience, as appropriate, the therapists will support and encourage the subject in emotional processing and resolution of whatever psychological material is emerging.
- u. Approximately two hours after drug administration during the second experimental session, prepare the subject for the blood draw for biomarker analysis. Bring in the phlebotomy technician when the subject is emotionally ready for the blood draw.
- v. Initiate the TASIT. The TASIT administration may be spread out between hours two and three to fit around the therapeutic process.
- w. Record any spontaneously reported reactions during the session.
- x. Provide water and electrolyte containing fluids throughout the session but not to exceed 3 L overall.
- y. Provide food during the latter part of the session.
- z. If it is appropriate to do so, initiate the first question of the C-SSRS at any point in the session if the subject is experiencing significant psychological distress that does not respond readily to processing with the therapists. The C-SSRS is required at least once during the session. It is preferable to administer it towards the end of the session, about six hours after the initial dose.
- aa. End the session if all medical and psychiatric parameters are acceptable and the subject is alert, ambulatory, and emotionally stable.

Post-drug:

- bb. The therapists will depart from the site when they have concluded that the subject is emotionally and medically stable. Therapists shall remain available to subjects during the experimental session and for one week after via 24 hour cellular phone for

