5.2.6 Biweekly Integrative Sessions

In addition to the integrative session the morning after each experimental session, the subject will have two additional integrative sessions with the therapists lasting 60 minutes

with the therapists between each experimental session scheduled at two-week intervals following the last integrative session. The therapists may conduct more or longer integrative sessions if they and the subject deem it necessary.

Activities for these sessions include integration of material that emerged as a part of experimental sessions and afterward into daily life. Therapists will emphasize their commitment to support the subject during the integration period and will be available via phone or pager.

During integrative sessions:

- a. Record each integrative session to audio and video. Subjects may receive access to copies of the recordings on a secure, password-protected website upon request.
- b. The C-SSRS will be administered just prior to beginning each integrative session.
- c. General wellbeing will be assessed at each integrative session.
- d. The subject and therapists will continue to work on supporting the subject as she or he considers his or her experiences during experimental sessions.
- e. The therapists will use clinical judgment to assess the subject's psychological wellbeing during this period of time. If there are any indications of continuing anxiety or distress, the therapists may arrange to work on reducing the distress at a specially scheduled integrative session, through continuing contact, or at the next regularly scheduled integrative session. The subject may also initiate contact with the therapists at any time throughout the study.
- f. At the second integrative session after the second experimental session, blood will be drawn for biomarker analysis.
- g. At the second integrative session after the second experimental session, collect information on phase of menstrual cycle for female subjects.
- h. At the beginning or end of each integrative session, subjects will complete:
 - a. BDI-II
 - b. STAI
- i. At the beginning or end of each integrative session, the IR will administer the LSAS.
- j. At the beginning or end of the third integrative session, subjects will also complete:
 - a. ERQ
 - b. TAS-20
 - c. TASIT
- k. Spontaneously reported reactions, AEs, and concomitant medications will be collected, as described in Section 8.5 and Section 9.0.

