- l. Assess status of symptoms at baseline specific to the study population.
- m. Remind the subject that the last integrative session in Stage 1 that this will be the last in-person visit prior to the 6-month Follow-up visit, and that some measures will be collected monthly by mail.
- n. Review how to use the Memory Aid Card with the subject. Subjects will use this card to record AEs, medications, and changes in psychiatric status that they will be asked about at the 6-month follow-up visit. Memory Aids will not be collected.

5.2.7 6-Month Follow-up

Subjects who have withdrawn from treatment but have continued for follow-up will also complete these assessments whenever possible. During the follow-up period:

- a. Subjects may return to taking psychiatric medications or change frequency or method of psychotherapy received from outside therapists if necessary.
- b. The following self-report measures will be completed by subjects and collected monthly at two, three, four, and five months after the second experimental session by mail:
 - a. BDI-II
 - b. STAI
 - c. PSS
- c. At the 6-month follow-up, an in-person visit will be conducted.
- d. The IR will administer the LSAS.
- e. Collect information on phase of menstrual cycle for female subjects.
- f. Blood will be drawn for biomarker analysis.
- g. Subjects will complete self-report outcome assessments, including:
 - a. ERQ
 - b. TAS-20
 - c. TASIT
 - d. QoL-Q
 - e. RSES
 - f. IRI
 - g. BDI-II
 - h. STAI
 - i. PSS
 - j. Feedback Questionnaire
- h. Review specified AEs and medications as described in Section 8.5 and Section 9.0. Subjects should bring the Memory Aid Cards to this visit, to be used as aids in recollection. These cards will not be collected.
- i. Assess status of symptoms at baseline specific to the study population.
- j. One of the therapists will assess suicidality with the C-SSRS.
- k. General wellbeing will be assessed.
- l. The therapists will review the responses to the Feedback Questionnaire assessing effects of the study with the subject. During the qualitative interview, additional follow-on questions may be asked to elucidate self-reported responses on the questionnaire.
- m. After all assessments are complete, the therapists will break the blind for the individual subject.
- n. Subjects who were randomized to the MDMA group will complete the termination visit at this time.

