The main estimates of effect size from blinded data will be conducted after the outcome measure assessments at the six-month follow-up are complete for all subjects. Data from all doses of MDMA during Stage 1 (n=16), to be compared with all data from placebo sessions (n=8), with each experimental session treated as an independent observation. The MDMA condition will encompass both Group 1 and Group 2 MDMA doses. Estimates of effect size will be obtained from BDI-II, STAI, PSS, IRI, RSES, ERQ, TAS-20, and QoL-Q scores collected pre-treatment, during and after each experimental session, and the follow-up period, with p value set at 0.05. Effect size will be used to determine the appropriate sample size for future studies.

Scores for BDI-II, STAI, PSS, IRI and RSES completed after each of the experimental session will be averaged to produce mean scores for these periods, including a post-experimental session 1 and post-experimental session 2 average score. BDI-II, STAI and PSS scores gathered via postal mail at monthly intervals from two to five months after the second experimental session will be averaged to produce mean scores for the follow-up period. Missing responses will be replaced with the sample average. These averages will be used for estimates of effect size.

TASIT scores will be compared assessing baseline, after experimental session 1, after experimental session 2, at integrative session six and at 6-month follow up. Correlations between TASIT scores and LSAS scores at the time point following each TASIT score will be made to see whether increased awareness of social cues is associated with reduced social anxiety. MDMA dose will be used as a covariate in order to examine the potential relationship between dose and changes in one or more variable, with dose (75, 100 or 125 mg) serving as the covariate.

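### The TASIT–LSAS pairing rule gives baseline TASIT an LSAS taken after the first blinded session, leaves the V13 and V14 pairs open to two readings, and is neither carried into nor withdrawn by the SAP

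*Protocol*

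**What the plan says.** Protocol section 12.0 first fixes the occasions: "TASIT scores will be compared assessing baseline, after experimental session 1, after experimental session 2, at integrative session six and at 6-month follow up". It then states the pairing: "Correlations between TASIT scores and LSAS scores at the time point following each TASIT score will be made". The declared purpose is to learn whether greater social awareness accompanies lower social anxiety. The next sentence makes MDMA dose (75, 100 or 125 mg) a covariate.

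The schedule is set elsewhere in the Protocol:

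- **Baseline LSAS.** Section 5.2.1 (screening): "A blinded IR will administer the LSAS".
- **Baseline TASIT.** Section 5.2.2: "At the end of the second preparatory session, subjects will complete the TASIT".
- **TASIT in the experimental sessions.** Section 5.2.3: "The TASIT administration may be spread out between hours two and three to fit around the therapeutic process".
- **TASIT after the sessions.** Section 5.2.6: "At the beginning or end of the third integrative session, subjects will also complete" a set of measures that includes the TASIT. The same section has the LSAS rated at the beginning or end of each integrative session.
- **All LSAS times.** Section 3.1: "at baseline, one day, two weeks, and one month after each experimental session, and at 6-month follow-up".
- **Six-month follow-up.** Section 5.2.7 has both measures at this visit. The blind is then broken, and "Subjects who were randomized to the MDMA group will complete the termination visit at this time".

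The SAP tests TASIT change from baseline to V13 (section 8.10.2) and from V13 to six months (section 8.10.2.1). Its exploratory section 8.10.3 correlates biomarkers with LSAS. It neither lists a TASIT–LSAS correlation nor says that the Protocol's has been withdrawn.

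**The concern.** The rule describes a lag, but the two instruments do not alternate regularly. LSAS is absent from all three preparatory visits, is dense after each session, and shares V13 and V14 with the TASIT. A single instruction to take the next LSAS therefore means different things at different visits.

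Two things are at stake. A pair that sets pre-treatment TASIT against post-session LSAS says nothing about whether a gain in social perception goes with a fall in anxiety. And because the pairing is not defined by visit, someone will have to define it once the data exist, in a study whose SAP (section 2.0) tests all comparisons without multiplicity correction.

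**Working it through.** There is no planned figure to reproduce: Protocol section 12.1 says that power estimates were not available. The check is to apply the rule to the schedule.

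**Inputs (Protocol Table 2, checked against sections 5.2.1 to 5.2.7)**

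- TASIT: V4, V6, V10, V13, V14.
- LSAS: V2, V7, V8, V9, V11, V12, V13, V14.
- The two occasions that section 12.0 places after the experimental sessions are taken as V6 and V10, because the TASIT is given within those sessions and at no other visit between V4 and V13.
- Integrative session six is V13, the sixth of V7, V8, V9, V11, V12, V13. Section 5.2.6 does not say which cycle its third integrative session belongs to, but Table 2 and sections 3.2 and 12.0 place this TASIT after session 2 only.

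**Mapping under both readings**

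| TASIT | LSAS strictly later | LSAS if same visit counts | Fits the stated aim? |
|---|---|---|---|
| V4 (baseline) | V7 | V7 | No, on either reading |
| V6 (session 1) | V7 | V7 | Yes, next day |
| V10 (session 2) | V11 | V11 | Yes, next day |
| V13 (one month) | V14 | V13 | Only if same visit counts |
| V14 (six months) | none in Stage 1 | V14 | Only if same visit counts |

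**Baseline pair.** The only LSAS before treatment is V2, which precedes V4. The next is V7, the day after the first blinded session (MDMA for 8 subjects, placebo for 4). Allowing same-visit pairs does not help, because there is no LSAS at V4.

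**V13 gap on the strict reading.** V13 falls 1 + 14 + 14 = 29 days after V10. V14 is six months, about 182.6 days, after V10. The gap is 182.6 − 29 = 153.6 days, and 153.6 / 30.4 = 5.05 months. During it, section 5.2.7 lets subjects resume psychiatric medication or change outside psychotherapy. This timing rests on Table 2 and agrees with the eight-month duration in section 4.1. Table 1 labels the first Stage 2 session Month 6, which does not fit a follow-up six months after V10.

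**V14 on the strict reading.** None of the 12 subjects has a later Stage 1 LSAS.

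**Covariate.** The dose values named for this analysis have no entry for the 4 placebo subjects. Elsewhere in section 12.0, for the exploratory plots and vital signs, dose includes 0 mg. MDMA subjects also change dose between sessions (Table 1), so none has a single dose value at V13 or V14.

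**Precision under any pairing.** By Fisher's z, the 95% interval around r = 0 with n = 12 is ± tanh(1.96 / √(12 − 3)) = ± tanh(0.653) = ± 0.57. With one covariate it is ± tanh(1.96 / √(12 − 4)) = ± tanh(0.693) = ± 0.60.

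**The case against.** The best defence is that *following* was meant to include the same visit. At V13 either measure may be given at the beginning or end of the session, so an LSAS can follow the TASIT that day. At V14 section 5.2.7 lists the LSAS before the TASIT, so there the defence needs *same time point* to count rather than literal order. The text does not exclude this. A reader might infer that three of the five pairs are already broken, but the documents support that only for the baseline pair. For V13 and V14 they show ambiguity.

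Four other strong readings also go too far:

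- **V14 TASIT paired with an open-label LSAS.** The next rating for a placebo subject who crosses over is V16, after open-label MDMA. But section 3.2 confines the TASIT objective to the Stage 1 comparison, and nothing suggests pairing across stages.
- **V7 LSAS used twice.** Correlating two predictors with one outcome is not an error.
- **Baseline pair confounded by treatment.** V4 TASIT precedes drug in a randomised trial, so in expectation it is independent of arm. Treatment adds variance to V7 LSAS but does not systematically confound the pair. Baseline-to-outcome prediction is a legitimate question, which section 12.0 asks of the TAS-20 with condition in the model. It is just not the question stated here.
- **The rule forbids change scores.** It says scores and is silent on change. The next sentence speaks of changes in variables, and the SAP (section 1.0) defines difference scores.

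It is also fair to say that the SAP does not list the correlation, that unlisted analyses may be run only as labelled post-hoc work (SAP sections 8.0 and 8.10.3), and that no stated decision depends on this result. That limits the importance. It does not settle which pairing applies, or whether the analysis was dropped.

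**Conclusion.** The point holds, as a minor one. One of the five pairs (V4 with V7) fails to test the stated aim however the rule is read. Two more (V13, V14) fail or succeed according to whether a same-visit LSAS counts, which the Protocol does not say. The remaining two are next-day pairs and work as intended, so a reader should not conclude that the whole set is uninformative. The SAP leaves the analysis in limbo.

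This rests on Table 2 as the operative schedule and on reading the two session occasions as V6 and V10. The correlation is exploratory, in a 12-subject pilot, and does not affect the primary LSAS analysis.

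**What to change.** Replace the rule with an explicit Stage 1 visit map and carry it into SAP section 8.10.3, or state there that the analysis is dropped.

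- **Baselines:** TASIT at V4, LSAS at V2. The map should name V4, because SAP section 8.6 takes baselines from the screening/baseline visit and the TASIT is first given later.
- **Pairs, as change from baseline on both scales:** TASIT V6 with LSAS V7, V10 with V11, V13 with V13, V14 with V14. Stage 1 data only. The V14 assessments precede unblinding.
- **Adjustment:** a partial correlation with Stage 1 arm as covariate. Arm is defined for all 12 subjects, which the named dose values are not. It also stops a drug effect on both scales from appearing as a correlation in the pooled sample.

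The cost is a few lines of wording, with no new visits or data. There are two limits. The V2 and V4 baselines are not same-day and may straddle the start of a medication taper, which Table 2 places at V3. And with 12 subjects the estimates will stay imprecise, so they should be reported with intervals and labelled exploratory.
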